6.2.5. Lung function

This section will describe the lung function of the patient at the baseline visit (visit 1).

Table 11. Baseline lung function (visit 1) - Treated Set (TS)

	Total
Time from spirometry to visit 1 (months)	
Mean (SD)	
95% CI	
Median (P25; P75)	
(Min; Max)	
N	
FVC (ml)	
Mean (SD)	
95% CI	
Median (P25; P75)	
(Min; Max)	
N	
FVC (%)	
Mean (SD)	
95% CI	
Median (P25; P75)	
(Min; Max)	
N	
FEV₁ (ml)	
Mean (SD)	
95% CI	
Median (P25; P75)	
(Min; Max)	
N	
FEV₁ (%)	
Mean (SD)	
95% CI	
Median (P25; P75)	

Table 11. Baseline lung function (visit 1) - Treated Set (TS)	
	Total
(Min; Max)	
N	
FEV₁/FVC	
Mean (SD)	
95% CI	
Median (P25; P75)	
(Min; Max)	
N	
mMRC Dyspnoea Scale n (%)	
Grade 0	
Grade I	
Grade II	
Grade III	
Grade IV	
GOLD classification of severity¹ n (%)	
GOLD 1 (Mild)	
GOLD 2 (Moderate)	
GOLD 3 (Severe)	
GOLD 4 (Very severe)	
GOLD version 2014² n (%)	
GOLD A	
GOLD B	
GOLD C	
GOLD D	
GOLD version 2017³ n (%)	
GOLD A	
GOLD B	
GOLD C	
GOLD D	

¹GOLD classification of COPD severity (based on post-bronchodilator FEV1): Mild: FEV₁ ≥ 80% of predicted value, Moderate: 50% ≤ FEV₁ < 80% of predicted value; Severe: 30% ≤ FEV₁ < 50% of predicted value; Very severe: FEV₁ < 30% of predicted value

² GOLD version 2014 group of patients: See **!Error! No se encuentra el origen de la referencia.**

³ GOLD version 2017 group of patients: See Figure 2

6.2.6. Concomitant diseases

This section will describe the concomitant diseases (CDs) of treated patients, and it will give details on whether they still have them on the date of the baseline visit (visit 1).

Table 12. Concomitant diseases at baseline visit (visit 1) - Treated Set (TS)			
	Total¹	Total with CDs²	Ongoing²
Does the patient present with any COPD-related concomitant diseases? n (%)			
Yes			
No			
Type of concomitant disease - Yes n (%)			
Cardiovascular disease			
Diabetes mellitus			
Musculoskeletal disorders			
Kidney diseases			
Liver diseases			
Osteoporosis			
Gastro-oesophageal reflux (GOR)			
Lung cancer			
Other ³			

Note: Concomitant disease (CD). A patient could have more than one CD

¹ Of the total number of treated patients (n=xx)

² Of the total number of patients with CDs (n=xx)

³ Other: AAA (n=x); BBB (n=xx); ...

In the ANNEX 3. RECORDED CONCOMITANT DISEASES, the diagnoses of the concomitant diseases, as well as their duration, will be specified.

6.2.7. Concomitant medication

This section will describe the indication of concomitant medication (CM) of treated patients, as well as the active substance and whether they continue with treatment after the baseline visit (visit 1).

Table 13. Concomitant medication at baseline visit (visit 1) - Treated Set (TS)			
	Total¹	Total with CM²	Ongoing²
Is the patient receiving any concomitant medication? n (%)			
Yes			
No			
Indication of the concomitant medication - Yes n (%)			
Indication 1			
Indication 2			
Indication 3			
...			

Note: Concomitant medication (CM). The same patient could have more than one CM

¹ Of the total number of treated patients (n=xx)

² Of the total number of patients with CM (n=xx)

Table 13. Concomitant medication at baseline visit (visit 1) - Treated Set (TS)

Total ¹	Total with CM ²	Ongoing ²
--------------------	----------------------------	----------------------

The medication for each of the indications, as well as its duration, will be specified in the ANNEX 4. CONCOMITANT MEDICATION.

6.2.8. Previous treatment for COPD

This section will describe previous treatments for COPD in the 6 months prior to the baseline visit (visit 1).

Table 14. Treatment for COPD in the 6 months prior to the baseline visit (visit 1) - Treated Set (TS)

	Total ¹	Total COPD ²	Ongoing ²
Has the patient received treatment for COPD in the previous 6 months? n (%)			
Yes			
No			
SAMA			
Yes			
No			
SABA			
Yes			
No			
LAMA			
Yes			
No			
LABA			
Yes			
No			
ICS			
Yes			
No			
LAMA/LABA n (%)			
Yes			
No			
LABA/ICS n (%)			
Yes			
No			
Other³			
Yes			
No			

NOTE: Patients treated with a LABA/LAMA combination (free and/or fixed combination) within the 6 previous months should not be selected for the study; the same applies to patients who continue with

Table 14. Treatment for COPD in the 6 months prior to the baseline visit (visit 1) - Treated Set (TS)

Total ¹	Total COPD ²	Ongoing ²
--------------------	-------------------------	----------------------

LABA/ICS treatment, who should not be treated in addition with Spiolto® Respimat® to prevent double-dosing of long-acting beta agonists (see section 4.1.2).

¹ Of the total number of treated patients (x = xx)

² Of the total number of patients who have received treatment for COPD in the previous 6 months (n=xx)

³ Other: AAA (n=x); BBB (n=x); ...

The drugs (active substance) for each one of the drug classes, as well as their duration, will be specified in the ANNEX 5. PREVIOUS TREATMENT FOR COPD.

6.2.9. Current treatment for COPD

This section will describe the current treatment for COPD that the patients will receive.

Table 15. Current treatment for COPD - Treated Set (TS)

	Total ¹	Total ²
Is the patient going to be treated with Spiolto® Respimat®? n (%)	---	---
Yes		
No		
Has the patient been trained properly on how to use Respimat®? n (%)	---	---
Yes		
No		
Is the patient going to receive other inhaled treatments for COPD? n (%)	---	---
Yes		
No		
Other inhaled treatments for COPD¹ n (%)		
SABA		
ICS		

NOTE: All treated patients must have received a dose of the study treatment

¹ Of the total number of patients (n=xxx)

² If the patient has received another treatment for COPD (n=xx)

The ANNEX 6. CURRENT TREATMENT FOR COPD will specify the concomitant medication prescribed for COPD and its duration.

6.3. DESCRIPTION OF THE SAMPLE AFTER 6 WEEKS (VISIT 2, TS)

This section will describe the follow-up of patients after 6 weeks of the study and the changes which occurred after 6 weeks of treatment with Spiolto® Respimat® (treatment for COPD, concomitant diseases and medication, smoking habit, etc.) of the Treated Set (TS) and those with data at the visit after 6 weeks (see *Table 4*).

6.3.1. Data after 6 weeks

This section will describe the number of patients who have completed their visit after 6 weeks (visit 2), the reason for discontinuation if they have not attended the visit and the time between visits (approx. 6 weeks).

Table 16. Continuation of the patient in the study after 6 weeks (visit 2) - Treated Set (TS)

	Total
Is the patient continuing in the study n (%)	
Yes	
No	
Lost to follow-up	
Does not meet inclusion/exclusion criteria	
Adverse event	
Protocol deviation	
Patient's decision	
Investigator's decision	
Other¹	
Time between visits (weeks)²	
Mean (SD)	
95% CI	
Median (P25; P75)	
(Min; Max)	
N	
Time to early termination (weeks)³	
Mean (SD)	
95% CI	
Median (P25; P75)	
(Min; Max)	
N	

¹Specify others: other 1 (n=x); other 2 (n=x); ...

² If the patient continues in the study (n=xx)

³ If the patient does not continue in the study (n=xx)

6.3.2. Treatment for COPD

This section will describe the continuity of the treatment received for COPD started at the baseline visit and the change in concomitant medication for COPD.

Table 17. Continuation of treatment with Spiolto® Respimat® after 6 weeks (visit 2) - Treated Set (TS)		Total n (%)
Is the patient continuing to receive the treatment with Spiolto® Respimat® started at the baseline visit?		
Yes		
No		
Reason why the patient is no longer receiving Spiolto® Respimat®¹		
Reason 1		
Reason ...		
Has the concomitant medication for COPD changed with respect to the last visit or is the patient receiving a new medication?		
Yes		
SABA		
ICS		
No		

¹ If the patient is no longer receiving the treatment with Spiolto® Respimat® started at the baseline visit (n=xx)

The ANNEX 6. CURRENT TREATMENT FOR COPD 6 will specify the new concomitant medication prescribed for COPD and its duration.

6.3.3. Concomitant diseases

This section will describe the presence of any new concomitant diseases with respect to those of the last visit.

Table 18. New concomitant diseases after 6 weeks (visit 2) - Treated Set (TS)		
	Total¹	Total with new CD²
Does the patient have any new concomitant diseases with respect to those of the last visit?		
n (%)		
Yes		
No		

Table 18. New concomitant diseases after 6 weeks (visit 2) - Treated Set (TS)

	Total ¹	Total with new CD ²	Ongoing ²
Type of new concomitant disease - Yes n (%)			
Cardiovascular disease			
Diabetes mellitus			
Musculoskeletal disorders			
Kidney diseases			
Liver diseases			
Osteoporosis			
Gastro-oesophageal reflux (GOR)			
Lung cancer			
Other ³			

Note: Concomitant disease (CD). A patient could have more than one CD

¹ Of the total number of treated patients (n=xx)

² Of the total number of patients with new CD (n=xx)

³ Other: AAA (n=x); BBB (n=x); ...

The ANNEX 3. RECORDED CONCOMITANT DISEASES will specify the diagnoses of new concomitant diseases, as well as their duration.

6.3.4. Concomitant medication

The additional intake of concomitant medication will be described in this section.

Table 19. Additional concomitant medication after 6 weeks (visit 2) - Treated Set (TS)

	Total ¹	Total with additional CM ²	Ongoing ²
Is the patient receiving any additional concomitant medication? n (%)			
Yes			
No			
Indication of the concomitant medication - Yes n (%)			
Indication 1			
Indication 2			
Indication 3			
...			

Note: Concomitant medication (CM)

¹ Of the total number of treated patients (n=xx)

² Of the total number of patients with additional CM (n=xx)

The additional medication for each of the indications, as well as its duration, will be specified in the ANNEX 4. CONCOMITANT MEDICATION.

6.3.5. Tobacco consumption

This section will describe whether the patient has changed his/her smoking habits since the last visit.

Table 20. Tobacco consumption after 6 weeks (visit 2) - Treated Set (TS)

	Total
Has he/she changed his/her smoking habits since the last visit? n (%)	
Yes	
No	
Change of smoking habit¹ n (%)	
He/she has quit smoking	
He/she is smoking less	
He/she is smoking more	
Number of cigarettes/day in patients who are smoking less	
Mean (SD)	
95% CI	
Median (P25; P75)	
(Min; Max)	
N	
Number of cigarettes/day in patients who are smoking more	
Mean (SD)	
95% CI	
Median (P25; P75)	
(Min; Max)	
N	

¹ Of the total number of patients who have changed their smoking habit (n=xx)

² Of the sample of patients who are ex-smokers and smokers in the visit after 6 weeks (n=xx). The pack-years value from the baseline visit is taken as the value in patients who have not changed their smoking habit

6.4. ANALYSIS OF EFFICACY (FAS)

This section will describe the results for the study's primary objective as well as for the secondary endpoints in **Full Analysis Set (FAS)**.

6.4.1. Analysis of primary endpoint

This section will describe the frequency and percentage of "Therapeutic success" at visit 2 (defined as: 10-point increase in the PF-10 score between the baseline visit (visit 1) and the visit after 6 weeks (visit 2) will be presented together with the 95% confidence interval.

Table 21. Therapeutic success after 6 weeks (visit 2) – Full Analysis Set (FAS)		
	Total n (%)	CI (95%)
Therapeutic success¹ n (%)		
Therapeutically successful		
Not therapeutically successful		

Therapeutic success: 10-point increase in the PF-10 score between visit 1 and visit 2.

¹ Of the total number of patients who have PF-10 data at the baseline visit (visit 1) and at the visit after 6 weeks (visit 2)

Figure 4. Therapeutic success after 6 weeks (visit 2) – Full Analysis Set (FAS)
[pie chart]

6.4.2. Analysis of secondary endpoints

This section will describe the data corresponding to the secondary efficacy endpoints.

Changes in PF-10 score

A descriptive analysis of the PF-10 score from the baseline visit (visit 1) to the visit after 6 weeks (visit 2), as well as the change (difference visit 2 - visit 1), will be conducted in this section.

Table 22. PF-10 score at baseline visit, after 6 weeks and change – Full Analysis Set (FAS)									
	n	mean	SD	(95% CI)	Median	[P25-P75]	Min	Max	P¹
Baseline PF-10									-
(Visit 1)									-
PF-10 after 6 weeks (Visit 2)									-
Change in PF-10 (v2-v1)									

¹ paired t-test /Wilcoxon Rank-Sum

Figure 5. PF-10 Score – Full Analysis Set (FAS)

[line/bar charts of the mean/median PF-10 at the baseline visit (visit 1) and the visit after 6 weeks (visit 2)]

Table 23. Change in PF-10 score according to therapeutic success – Full Analysis Set (FAS)

	n	mean	SD	(95% CI)	Median	[P25-P75]	Min	Max	P ¹
Baseline PF-10 (visit 1)									
Therapeutically successful									
Not therapeutically successful									
PF-10 after 6 weeks (visit 2)									
Therapeutically successful									
Not therapeutically successful									
Change in PF-10 (v2-v1)									
Therapeutically successful									
Not therapeutically successful									

¹ independent two-sample t-test/Mann–Whitney U test

Figure 6. PF-10 score according to therapeutic success – Full Analysis Set (FAS)

[line/bar charts of the mean/median PF-10 at the baseline visit (visit 1) and the visit after 6 weeks (visit 2)]

according to therapeutic success]

Patient's general condition - PGE score

A descriptive analysis of the PGE score at the baseline visit (visit 1) and the visit after 6 weeks (visit 2) will be conducted in this section, to assess the patient's general condition according to the investigator, using an 8-point ordinal scale from 1 (very poor) to 8 (excellent).

Table 24. General condition of the patient – PGE score as assessed by the physician at the baseline visit and after 6 weeks in completed patients – Full Analysis Set (FAS)

	Baseline (Visit 1)	6 weeks (Visit 2)	P ¹
PGE score n (%)			
1			
2			

Table 24. General condition of the patient – PGE score as assessed by the physician at the baseline visit and after 6 weeks in completed patients – Full Analysis Set (FAS)

	Baseline (Visit 1)	6 weeks (Visit 2)	P ¹
3			
4			
5			
6			
7			
8			
Pooled PGE Score n (%)			
Poor (1-2)			
Satisfactory (3-4)			
Good (5-6)			
Excellent (7-8)			

¹ McNemar test

Figure 7. Patient's general condition –PGE score as assessed by the physician – Full Analysis Set (FAS)

[bar chart of PGE score at the baseline visit (visit 1) and the visit after 6 weeks (visit 2)]

[bar chart of pooled PGE score at the baseline visit (visit 1) and the visit after 6 weeks (visit 2)]

Patient satisfaction with Spiolto® Respimat®

A descriptive analysis of patient satisfaction with Spiolto® Respimat® after 6 weeks of treatment (visit 2) will be conducted in this section, using a 7-point ordinal scale, from 1 (very satisfied) to 7 (very dissatisfied).

Table 25. Patient satisfaction with Spiolto® Respimat® after 6 weeks of treatment (visit 2) in completed patients - Full Analysis Set (FAS)

	Total n (%)
Patient overall satisfaction with inhalation with the Spiolto® Respimat® treatment	
Very unsatisfied	
Unsatisfied	
Rather unsatisfied	
Neither satisfied, nor unsatisfied	
Rather satisfied	
Satisfied	
Very satisfied	

Table 25. Patient satisfaction with Spiolto® Respimat® after 6 weeks of treatment (visit 2) in completed patients - Full Analysis Set (FAS)

	Total n (%)
Patients satisfaction with inhaling from Respimat® device?	
Very unsatisfied	
Unsatisfied	
Rather unsatisfied	
Neither satisfied, nor unsatisfied	
Rather satisfied	
Satisfied	
Very satisfied	
Patients satisfaction with haling of the Respimat® inhalation device?	
Very unsatisfied	
Unsatisfied	
Rather unsatisfied	
Neither satisfied, nor unsatisfied	
Rather satisfied	
Satisfied	
Very satisfied	

¹ Chi-square test/Fisher's exact test

Figure 8. Patient satisfaction with Spiolto® Respimat® – Full Analysis Set (FAS)
[cumulative bar charts for the three items]

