5.2.3. Analysis of primary endpoint

For the primary endpoint, the proportion of patients with therapeutic success at visit 2 i.e., approximately 6 weeks (define as 10-point increase in the PF-10 score between visit 1 and visit 2) together with the 95% confidence interval will be presented.

***PF-10** is a sub-domain of SF-36 and consists of 10 items evaluating the scope of the restrictions experienced when carrying out routine activities. Each PF-10 item may be answered with “yes, limited a lot”, “yes, limited a little”, or “no, not limited at all”, with a score of 1, 2 or 3. The scores of the 10 items are added up, resulting in a value between 10 (a patient who answers all questions with “yes, limited a lot”) and 30 (a patient who answers all questions with “no, not limited at all”). The final sum of the individual scores will be standardised to a range of 0 to 100 using the following formula: $100 \times (\text{sum} - 10) / 20$.¹

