5.2.7. Statistical methodology

In this observational study, cross-sectional data will be collected at the start of the study and longitudinal follow-up data will be collected in the 6-week period for patients with COPD disease requiring dual bronchodilator therapy in routine clinical practice.

Baseline data will be described using a cross-sectional approach. Longitudinal follow-up data will be summarised descriptively. Due to the observational nature of this study, it is not planned to carry out (confirmatory) hypothesis testing in a strict statistical sense. Analyses are descriptive in nature and confidence intervals and p-values from statistical models will be used for exploratory purposes. No adjustments for multiple testing will be carried out in the statistical significance evaluation. Consequently, significant differences may be observed by chance along and p-values should be interpreted as exploratory and treated with caution. No formal hypothesis testing will be performed as this is a self-controlled study.

The statistical characteristics presented in the results tables will include: N (total number of valid values), mean, standard deviation (SD), 95% confidence interval of the mean (95% CI), median, 25th and 75th percentiles (P25 and P75, respectively), minimum and maximum (min and max, respectively) for continuous endpoints. The categorical endpoints will be described by their absolute and relative frequencies. The proportion rates and the 95% CIs will be provided when appropriate.

For the primary endpoint, the proportion of patients with therapeutic success at visit 2 (a 10-point increase in the PF-10 score between visit 1 and visit 2) together with the 95% confidence interval will be presented.

For the secondary endpoints:

- Changes in PF-10 score from visit 1 to visit 2
- Patient's general condition assessed by the physician (PGE score) at visit 1 and visit 2.
- Patient satisfaction with Spiolto® Respimat® at visit 2.

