The patient's general condition (PGE score) at visit 1 and visit 2, the mMRC at visit 1 and patient satisfaction at visit 2 are categorical endpoints, so they will be analysed in frequency tables. The change from visit 1 to visit 2 in the PF-10 score is a continuous assessment criterion, so it will be analysed by: n (total number of valid values), mean, standard deviation (SD), 95% confidence interval of the mean (95% CI), median, 25th and 75th percentiles (P25 and P75, respectively), minimum and maximum (min and max, respectively).

Changes in the PF-10 between visit 1 and visit 2 will be analysed using a paired t-test or the non-parametric Wilcoxon Rank-Sum Test for data with non-normal distribution). Changes in the PGE between visit 1 and visit 2 will be analysed using McNemar test.

Data on safety will be reported according to local requirements. Statistical analyses and reporting of adverse reactions (ARs)/adverse events (AEs) will be descriptive in nature. The incidences of ARs and AEs will be analysed in relation to the number of treated patients.

Every effort will be made to collect complete data at the specified study visits (see DMP). Any data removed from the analysis will be documented, recording the site and the patient number, as well as the reason for the removal (see the ANNEX 1. DB DEBUGGING).

A statistical significance level of 0.05 will be applied in all the statistical tests. The evaluation will be carried out using SAS® software, version 9.4 or later.

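### SAP Table 23 tests PF-10 change between groups defined by a cut-off on that same change, so the change-row p-value is near zero by construction at any plausible success rate.

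*SAP*

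**What the plan says.** SAP 5.2.3 makes therapeutic success at visit 2 the primary endpoint, "define as 10-point increase in the PF-10 score between visit 1 and visit 2". The note under Table 21 in SAP 6.4.1 repeats it: "Therapeutic success: 10-point increase in the PF-10 score between visit 1 and visit 2".

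SAP 6.4.2 then describes PF-10 at each visit, "as well as the change (difference visit 2 - visit 1), will be conducted in this section". Two tables follow.

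- Table 22 shows the whole Full Analysis Set. Its P column is footnoted "paired t-test /Wilcoxon Rank-Sum", and its baseline and visit 2 rows are marked with a dash, so only the change row is tested.
- Table 23 shows baseline, visit 2 and change, each split by success status. Its P column is footnoted "independent two-sample t-test/Mann–Whitney U test". No row carries a dash.

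SAP 5.2.7 says that PF-10 change will be "analysed using a paired t-test or the non-parametric Wilcoxon Rank-Sum Test for data with non-normal distribution". It sets a 0.05 level for all tests, describes the analyses as exploratory, and adds: "Consequently, significant differences may be observed by chance along and p-values should be interpreted as exploratory and treated with caution".

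**The concern.** In the change row of Table 23, the variable tested is the variable that forms the groups. Every success has a larger change than every non-success, by definition. A two-sample test there asks whether patients selected for a large change had a larger change than the rest, and the answer is known before any data are collected.

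The table sits in the efficacy section of a single-cohort study with no control group. A very small p-value in that place can be read as support for the product, although it would also appear if PF-10 did not change on average, or fell.

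**Working it through.** **Inputs.** From SAP 4.2: 900 evaluable patients and 50% success. From SAP 5.2.7: significance level 0.05, taken here as two-sided because the side is not stated. From SAP 5.2.3: a 0-100 scale built from ten items scored 1 to 3, so complete answers move it in 5-point steps (100/20). The SD of PF-10 change is not in the documents and is assumed to be 5 to 25 points.

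**The plan's own figure.** 1.96 × sqrt(0.5 × 0.5 / 900) = 0.0327, giving 46.7% to 53.3%. 900 / (1 − 0.10) = 1000. Both match SAP 4.2.

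**Separation.** If success means change ≥ 10, all non-successes have change < 10. If it means change > 10, all non-successes have change ≤ 10. Under either reading the groups share no value.

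**Mann-Whitney z under complete separation.** With group sizes a and b and N = a + b, U differs from its null mean by ab/2, so z = (ab/2) / sqrt(ab(N+1)/12) = sqrt(3ab/(N+1)). At N = 900:

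| Successes v non-successes | 3ab/901 | z | Normal-approximation p |
|---|---|---|---|
| 450 v 450 (planned) | 674.3 | 26.0 | about 1e-148 |
| 90 v 810 | 242.7 | 15.6 | about 1e-54 |
| 45 v 855 | 128.1 | 11.3 | about 1e-29 |
| 2 v 898 | 5.98 | 2.45 | 0.014 |

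Ties here occur only within groups. They shrink the variance and leave the numerator unchanged, so a tie correction would raise these z values.

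**No mean change.** PF-10 change was simulated on a 5-point grid with mean 0, N = 900 and 300 runs per row, and split at ≥ 10:

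| Assumed SD of change | Share of successes | Largest p, t-test | Largest p, Mann-Whitney |
|---|---|---|---|
| 5 | 6.7% | 4e-46 | 6e-28 |
| 10 | 22.7% | 4e-133 | 8e-96 |
| 15 | 30.8% | 1e-153 | 2e-116 |
| 20 | 35.5% | 3e-166 | 3e-127 |
| 25 | 38.3% | 6e-173 | 5e-134 |

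A second simulation kept scores within 0-100 (assumed mean 45-60, SD 20-30, between-visit correlation 0.6-0.95; 400 runs per setting). The change row rejected in every run, in all 45 settings with ≥ 10 and all 30 with > 10. A paired t-test on data generated with no mean change rejected in 4.0% to 5.9% of runs (12 settings, 1000 runs each), as it should.

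**Mean worsening.** With mean change −10 and SD 10, successes fall to 4.0% and the largest p is 2e-27 (t-test) and 9e-15 (Mann-Whitney).

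**Where it breaks down.** With mean change −10 and SD 5, almost nobody gains 10 points: the t-test could not be computed in 292 of 300 runs, and the Mann-Whitney p reached 0.011.

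**The case against.** **Status of the test.** The strongest reply is that nothing rests on this cell. SAP 5.2.7 rules out formal hypothesis testing and asks for caution with p-values. Both Table 23 groups received the drug. The two-sample test for PF-10 appears only in this footnote of an empty table shell, and footnotes elsewhere are loosely kept: Table 25 has a test footnote and no P column. This limits the harm but does not remove the problem. Table 23 does have a P column and exempts no row, while Table 22 does exempt rows. The caution in SAP 5.2.7 concerns differences arising by chance, whereas this one is fixed in advance.

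**A near-zero p whatever the drug does.** A reader might infer this. It goes too far: when only a few of about 900 patients reach the cut-off, the p-value can be merely small or impossible to compute. At 2 v 898 it also depends on the method: 0.014 by the normal approximation, but 2/C(900,2), about 5e-6, by the exact test without ties. These cases are remote from the 50% that SAP 4.2 assumes.

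**All of Table 23 equally void.** A reader might infer this too. Baseline and visit 2 PF-10 are components of the change, so those comparisons are coupled to the grouping, but the groups can overlap there. With no mean change, simulated rejection ran from 44% to 100% at baseline and 35% to 100% at visit 2 over the assumed means, SDs and correlations. Baseline fell to 4-5% when change was generated independently of baseline. The documents give none of these inputs, so no rate can be asserted.

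**Conclusion.** The point holds for the change row of Table 23. At about 900 patients and any plausible success rate, its p-value is near zero by construction and carries no information about treatment. The separation itself needs no assumption about SD, correlation or the exact reading of the cut. Only the size of the p-value depends on how many patients fall in each group.

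The consequence is confined to one exploratory p-value in one secondary table. The success proportion and its confidence interval (Table 21), the within-patient change (Table 22) and the sample size are unaffected by this circularity. The change should be made because the p-value is wrong as planned and costs nothing to remove. It is not a threat to the primary result.

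A separate point of naming affects Table 22. Rank-sum is the usual name of the unpaired Wilcoxon test, while the comparison there is within patients.

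**What to change.** 1. In Table 23, remove the p-value from the change row, for example with a dash as Table 22 does for its untested rows. Keep the descriptive statistics.
2. Add a note under Table 23: *Groups are defined by the PF-10 change shown; differences between them are not evidence of a treatment effect.*
3. Optional: drop the baseline and visit 2 p-values, and with them the column and footnote, or extend the note to those rows.
4. Separately, in SAP 5.2.7 and the Table 22 footnote, replace the rank-sum name with the paired Wilcoxon signed-rank test.

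The cost is one deleted p-value, one sentence and one test name corrected in two places. No new data or analysis is needed. The deletion conflicts with nothing in SAP 5.2.7 or Protocol 9.7.1, since neither calls for a two-sample test of PF-10.
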